3.0 OBJECTIVES/AIMS

Study Objectives

Primary: To evaluate the hemodynamic effectiveness of Ang II (Giapreza) for intraoperative and postoperative hypotension in kidney transplant patients. This will be evaluated by the time to reaching BP goal.

Secondary: To evaluate the safety of Ang II (Giapreza) for intraoperative and postoperative hypotension in kidney transplant patients. This will be evaluated by collecting the incidence of common adverse events (ADE) seen from other Ang II (Giapreza) studies in this patient population.

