6.0 STUDY DESIGN AND PROCEDURES

This will be a single-center, prospective, observational study.

The prospective, observational study will include 20 consecutive patients receiving DDKT requiring intraoperative or postoperative vasopressors to assess the hemodynamic efficacy and safety and efficacy of Ang II (Giapreza).

The care process for this study of Ang II (Giapreza) in deceased donor kidney transplants (DDKT) at University of Illinois Hospital and Health Sciences (UIHHSS) will follow the exact same procedure as described above except (in bold and red):

PRE-TRANSPLANT – n/a DURING TRANSPLANT

- The transplant operation begins.
- If intraoperative hypotension occurs (e.g. SBP < 120 mmHg) the attending surgeon and attending anesthesiologist will:
 - Give blood products first if patient bleeding
 - If not bleeding or hypotensive despite blood products, intravenous fluids will be given
 - If hypotensive despite intravenous fluids then the attending surgeon and attending anesthesiologist will assess for cardiogenic shock and if suspected give inotropes
 - If not in cardiogenic shock and hypotensive despite fluids (+/- inotropes) then Ang II (Giapreza) will be initiated as the first vasopressor given for the treatment of distributive shock.
 - Ang II (Giapreza) will be titrated intraoperative to achieve goal BP.
 - Ang II (Giapreza) will be initiated following the FDA approved dosing in the package insert. This dosing includes a starting dose of 20 nanograms ng/kg/min. Titration will occur every 5 minutes by increments of up to 5 ng/kg/min as needed. During the first 3 hours, the maximum dose will not exceed 80 ng/kg/min. Maintenance dose will n exceed 40 ng/kg/min. Administration through a central venous line will be recommended.
 - If the maximum dose of AT II (Giapreza) is reached (80 ng/kg/min in the first 3 hours or 40 ng/kg/min thereafter), additional vasopressor selection and management will be at the discretion of the attending surgeon and attending anesthesiologist.
 - If additional vasopressors are needed beyond Ang II (Giapreza), all other vasopressors will be titrated off first.
 - If the patient is unable to be titrated off the Ang II (Giapreza) intraoperatively, they will be continued postoperatively in the Intensive Care Unit (ICU) and titrated until the patients' blood pressure is stable without vasopressor support.
- If distributive shock does NOT occur intraoperatively, Ang II (Giapreza) will NOT be initiated.

AFTER TRANSPLANT

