- If the patient is unable to be titrated off the Ang II (Giapreza) intraoperatively, they will be continued
 postoperatively in the Intensive Care Unit (ICU) and titrated until the patients' blood pressure is stable
 without vasopressor support.
- If the patient never received Ang II (Giapreza) intraoperatively and postoperative hypotension occurs (e.g. SBP < 120 mmHg) the attending surgeon or ICU team will:
 - Give blood products first if patient bleeding
 - If not bleeding or hypotensive despite blood products, then intravenous fluids will be given

- If hypotensive despite intravenous fluids then the attending surgeon and attending anesthesiologist will assess for cardiogenic shock and if suspected give inotropes
- If not in cardiogenic shock and hypotensive despite fluids (+/- inotropes) then Ang II (Giapreza)
 will be given as the first line vasopressor for the treatment of distributive shock.
- Ang II (Giapreza) will be titrated postoperatively to achieve goal BP and titrated until the patients' blood pressure is stable without vasopressor support.
 - Ang II (Giapreza) will be initiated following the FDA approved dosing in the package insert. This dosing includes a starting dose of 20 nanograms ng/kg/min. Titration will occur every 5 minutes by increments of up to 5 ng/kg/min as needed. During the first 3 hours, the maximum dose will not exceed 80 ng/kg/min. Maintenance dose will n exceed 40 ng/kg/min. Administration through a central venous line will be recommended.
 - If the maximum dose of AT II is reached (80 ng/kg/min in the first 3 hours or 40 ng/kg/min thereafter), additional vasopressor selection and management will be at the discretion of the attending surgeon and attending anesthesiologist.
 - If additional vasopressors are needed beyond Ang II (Giapreza), all other vasopressors will be titrated off first.
 - If at any point the treating physician feels there is a safety concern with the study drug it can be discontinued immediately.
- Ang II (Giapreza) and other vasopressor medications (if applicable) will be titrated
 postoperatively to achieve goal BP and titrated until the patients' BP is stable without
 vasopressor support.
- If distributive shock does NOT occur postoperatively, Ang II (Giapreza) will NOT be initiated

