- -Type I
- -Type II

Intraoperative Hemodynamic Data Points:

- -Intraoperative BP (SBP, DBP, MAP) every 5 minutes
- -Intraoperative heart rate every 5 minutes
- -Maximum dose of Ang II (Giapreza) (ng/kg/min)
- -Duration of Ang II (Giapreza) (hours)
- -Number of intraoperative vasopressors (if applicable)
- -Intraoperative agents used in addition to Ang II (Giapreza) (if applicable)
- -Dopamine (Y/N)
- -Norepinephrine (Y/N)
- -Epinephrine (Y/N)
- -Phenylephrine (Y/N)
- -Vasopressin (Y/N)
- -Minimum intraoperative SBP and DBP (mmHg)
- -Minimum intraoperative HR (bpm)

- -Intraoperative volume resuscitation (L)
- -Type of crystalloid and volume: 0.9% NaCl, PlasmaLyte, Lactated Ringers (L)
- -Type of colloids and volume: Albumin, Hydroxyethyl Starch, Mannitol (L)
- -Intraoperative blood product utilization (volume and type of blood products administered)

Post-operative Hemodynamic Data Points:

- -Postoperative BP (SBP, DBP, MAP mmHg) every 1 hour for the first 72 hours or duration of vasopressors (whichever is longer) after transplant
- -Postoperative HR (bpm) every 1 hour for first 72 hours or duration of vasopressors (whichever is longer) after transplant
- -Maximum dose of postoperative Ang II (Giapreza) ng/kg/min
- -Maximum dose of postoperative other vasopressors (in norepinephrine equivalents if applicable)
- -Starting dose of postoperative Ang II (Giapreza) and other vasopressors (in norepinephrine equivalents if applicable)
- -Duration of postoperative vasopressors (hours if applicable)
- -Number of postoperative vasopressors (if applicable)
- -Minimum postoperative BP (SBP, DBP, MAP mmHg) in first 72 hours after transplant (in first 24hrs, second 24hrs, third 24 hrs, and total 72hrs)
- -Minimum postoperative HR (bpm) in first 72 hours after transplant (in first 24hrs, second 24hrs, third 24 hrs, and total 72hrs)
- -Maximum postoperative BP (SBP, DBP, MAP mmHg) in first 72 hours after transplant
- -Maximum postoperative HR (bpm) in first 72 hours after transplant
- -Postoperative agents used:
- -Dopamine
- -Norepinephrine
- -Epinephrine
- -Phenylephrine
- -Vasopressin
- -Postoperative volume resuscitation (L in the first 24hrs, 48hrs, 72hrs)
- -Daily intake volume (milliliters) during ICU admission
- -Daily urine output volume (milliliters) during ICU admission
- -Postoperative blood product utilization (volume and type of blood products administered during ICU admission after operating room)

Post-operative Clinical Data Points:

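### BP is captured every 5 minutes in the operating room but hourly after surgery, so time to BP goal is known only to within about 60 minutes for patients who start Ang II postoperatively

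*Combined protocol and SAP*

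**What the plan says.** Section 3.0 states the primary objective for hypotension both during and after surgery: "This will be evaluated by the time to reaching BP goal".

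Section 6.0 lets treatment begin in either setting. The After Transplant steps cover a first start in the ICU ("If the patient never received Ang II (Giapreza) intraoperatively and postoperative hypotension occurs"). An infusion begun in the operating room may also carry over: "If the patient is unable to be titrated off the Ang II (Giapreza) intraoperatively, they will be continued" after surgery.

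The BP fields in Section 6.0 depend on location. The intraoperative list has "Intraoperative BP (SBP, DBP, MAP) every 5 minutes"; the postoperative list has "Postoperative BP (SBP, DBP, MAP mmHg) every 1 hour for the first 72 hours", or for as long as vasopressors run if that is longer.

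The postoperative dosing text in the same section reads "This dosing includes a starting dose of 20 nanograms ng/kg/min", "Titration will occur every 5 minutes by increments of up to 5 ng/kg/min as needed" and "During the first 3 hours, the maximum dose will not exceed 80 ng/kg/min".

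Neither the clock time of Ang II start nor a directly recorded time of reaching goal is a listed field. Section 9.0 names no method for interval-censored times or for combining the two reading schedules.

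**The concern.** The endpoint is a time measured in minutes, and in one of its two named settings the planned readings are an hour apart. For a postoperative starter, or a patient who leaves the operating room before reaching goal, the data show only that the goal was reached between two hourly readings, or between drug start and the first reading. If the first reading at goal is taken as the event time, the recorded time is too long, and by far more after surgery than during it.

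This is a 20-patient convenience pilot (Section 12.0), so no test decision is at stake. What is at stake is the estimate the study exists to produce. A gap between operating room and ICU could be read as a difference in drug effect when it comes from the reading schedule. Section 7.0 expects the results to lead to further studies.

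**Working it through.** The plan gives no precision figure for this endpoint to reproduce. Its one derived planning number, 40 consented for 20 treated, follows from 20 / 0.50 = 40 and does not bear on this point.

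**Inputs from the documents.** Reading interval g = 5 min in the operating room and g = 60 min afterwards; 5-minute titration from 20 to at most 80 ng/kg/min; 20 treated patients (all Section 6.0).

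**Assumptions, not in the documents.** True median time to goal of 5, 10, 20 or 30 min; exponential times, with lognormal as a check; start time known; starts spread evenly between readings; one crossing of the goal that persists. A range is used because no expected time in transplant recipients is given. The 5-minute median in Section 2 comes from a phase 3 trial that Section 7.0 describes as mostly septic shock.

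**Time scale.** (80 − 20) / 5 = 12 steps; 12 × 5 min = 60 min at the fastest. A patient titrated over the whole stated range could therefore have a single planned BP value during that course.

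**Recording delay.** Recorded time = T + V, where T is the true time and V, the wait for the next reading, is uniform on (0, g). Mean delay = g/2: 30 min hourly, 2.5 min on 5-minute readings, whatever the distribution of T.

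**Recorded medians.** Solve P(T + V ≤ x) = 0.5 with T exponential and rate λ = ln 2 / median. The share at goal by the first hourly reading is 1 − (1 − e^(−60λ)) / (60λ).

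| True median (min) | Recorded, hourly | Recorded, 5-min | Gap | At goal by first hourly reading |
|---|---|---|---|---|
| 5 | 37.2 | 7.6 | 29.5 | 88% |
| 10 | 43.7 | 12.6 | 31.2 | 76% |
| 20 | 54.5 | 22.5 | 32.0 | 58% |
| 30 | 63.4 | 32.5 | 30.9 | 46% |

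Gaps are taken before rounding. For patients in the last column only an upper bound is known. Lognormal times give similar hourly medians: 36.8, 43.2, 54.3 and 64.1 min (log SD 0.8), and 35.4, 40.9, 51.6 and 62.1 min (log SD 0.4).

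**Pooled median of 20 patients.** Average sample median over simulated trials, shown as the shift from all patients starting in the operating room:

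| Postoperative starters | True 10, exponential | True 20, exponential | True 10, lognormal, log SD 0.4 |
|---|---|---|---|
| 2 | +1.4 | +2.4 | +0.5 |
| 5 | +4.4 | +6.8 | +1.7 |
| 10 | +12.4 | +15.6 | +6.4 |
| 20 | +30.7 | +31.2 | +28.2 |

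**Does interval-censoring help?** At a true median of 10 min with 10 of 20 patients read hourly, the Turnbull median averages 10.2 (exponential), 9.8 (log SD 0.8) and 10.0 (log SD 0.4), against 25.2, 23.5 and 19.1 uncorrected. With all 20 hourly it averages 11.7, 11.4 and 10.7, against 44.1, 43.3 and 40.9. An exponential interval-censored fit is less safe: with log SD 0.4 it gives 7.0 (10 of 20 hourly) and 6.1 (all hourly).

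**The case against.** The strongest reply is that Section 6.0 only lists data points. Nowhere does the plan say that time to goal will be read off the hourly series. Staff titrating every 5 minutes presumably check BP more often than hourly, and data are extracted by hand from the electronic record, so denser values may exist. That is fair about the record, but not about the plan, which commits to hourly values only. If denser values exist, the fix is nearly free. The start time is probably retrievable too, since infusion duration and the relatedness definitions in Section 11.0 both need it.

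Other points limit the size of the claim, and they stand:

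- Sixty minutes is an upper bound on the interval. Its mean width is about 36 min at a true median of 5 min.
- The gap depends on when starts fall. At a true median of 5 min, the hourly recorded median is about 13.6 min if starts cluster in the 15 minutes before a reading and about 52.5 min if they cluster in the 15 minutes after one. Against 7.6, the gap is then about 6 to 45 min.
- The bias needs an analysis that takes the first reading at goal as the event time. Section 9.0 does not say so, but it names no alternative.
- The number of postoperative starters is unknown, and the effect of patients who cross from operating room to ICU was not estimated.
- The plan gives no numeric BP goal and no rule for sustained attainment, so the minute-level figures are illustrative.

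None of these removes the 12-fold difference in reading interval (60 / 5) within one primary endpoint.

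**Conclusion.** The concern holds. As planned, the primary endpoint is measured coarsely, and if first readings are used it is shifted upward, in one of its two named settings. Under evenly spread starts the false gap between settings is 29.5 to 32.0 min for true medians of 5 to 30 min; uneven starts could make it much smaller or larger. Reporting by setting displays the distortion but does not remove it. A pooled median is barely affected with 2 postoperative starters and substantially affected with 10 or more in most of the scenarios tried. It should be corrected before data are extracted; the harm is a misleading estimate, not a wrong test decision.

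**What to change.** In the BP fields of Section 6.0, let capture follow the infusion and not the location. From Ang II start until BP goal is reached, another vasopressor is added or Ang II is stopped, extract BP every 5 minutes or every charted or monitor value, in the operating room or ICU. Keep the hourly values after that. Add as fields the clock times of Ang II start and of each added vasopressor.

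In Section 9.0, state that where only sparser values exist the time is interval-censored between the last reading below goal (or drug start) and the first at goal. Use a Turnbull estimate or a flexible parametric model, not an exponential fit. Report by setting of Ang II start, with the number in each and the number who have hourly readings only.

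The cost is a few time fields and extra extraction over a short period in 20 patients. Someone must confirm that the software named in Section 6.0 can fit interval-censored times. Interval-censoring cannot restore precision: for 10 postoperative starters at a true median of 10 min, 95% of Turnbull estimates fall between 2.2 and 30.9 min with hourly readings, against 2.7 to 20.1 min with 5-minute readings. Denser extraction is therefore the main remedy and the censored analysis the fallback. Dosing and care are unchanged.

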2. BACKGROUND/SCIENTIFIC RATIONALE

The inability to meet blood pressure (BP) goals in the intraoperative and postoperative period of kidney transplantation carries significant consequences, the most serious of which is hypoperfusion to the newly transplanted organ leading to graft failure (Aulakh 2015, Campos 2012, Toth 1998). Following kidney transplant, it is of utmost importance to maintain adequate perfusion to the kidney allograft for optimal function. This adequate perfusion is maintained by the maintenance of adequate systemic blood pressure. Periods of hypotension in the recipient in the intraoperative and postoperative period can have detrimental effects such as acute tubular necrosis (ATN) leading to delayed graft function or even allograft loss (Walsh 2013). In the intraoperative and postoperative setting of kidney transplantation fluid-refractory hypotension (i.e. distributive shock) is primarily reversed by catecholamine vasopressors - phenylephrine, norepinephrine, epinephrine, and dopamine) (Dandan 2019). Unfortunately, animal and human models have demonstrated that the use of catecholamine vasopressors may cause a reduction in renal blood flow, increase in incidence of acute kidney injury (AKI), and worsen clinical outcomes (Busse 2019). It is known that catecholamine vasopressors predominantly vasoconstrict the afferent arteriole of the kidneys and this vasoconstriction can lead to ischemia at the kidney and in a perioperative kidney transplant patient, putting the new allograft at risk for injury and failure by decreasing blood flow to the new allograft. It has been found that perioperative catecholamine usage is associated with decreased urine output after kidney transplantation (Choi 2016), slower normalization of recipient serum creatinine (Day 2014), delayed graft function in recipients (Robert 2010, Day 2014), increased rate of rejection (Choi 2016), increased rate of tachycardias (Robert 2010), increased length of stay, and increased mortality (Choi 2016, Ciapetti 2009). Despite these known risks, no advances have been made in the pharmacologic treatment of intraoperative or perioperative hypotension in decades. As such, there is an urgent need to identify safer and more effective pharmacologic therapies to manage intra- and post-op hypotension/hypoperfusion in the renal transplant population.

Need for the Study

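### Postoperative urine output, intake and blood products are recorded only during the ICU stay, so how long they are observed depends partly on how long the patient needs vasopressors

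*Combined protocol and SAP*

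**What the plan says.** The data list in Section 6.0 (Post-operative Hemodynamic Data Points) limits three items to the ICU stay and gives no number of days for any of them:

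- "Daily intake volume (milliliters) during ICU admission"
- "Daily urine output volume (milliliters) during ICU admission"
- postoperative blood products, described as "volume and type of blood products administered during ICU admission after operating room"

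Other items in the same list carry no location limit. Postoperative blood pressure and heart rate are hourly for 72 hours, or for as long as vasopressors run if that is longer. Fluids are listed as "Postoperative volume resuscitation (L in the first 24hrs, 48hrs, 72hrs". Under Post-operative Clinical Data Points, creatinine, creatinine clearance and GFR are daily after surgery, also without an ICU limit. Blood products given in the operating room are a separate item.

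On the ICU itself, Section 6.0 says of patients who cannot come off Ang II during surgery that "they will be continued postoperatively in the Intensive Care Unit (ICU) and titrated until" blood pressure is stable without vasopressors. No section gives an ICU admission or discharge rule, or says where a patient weaned in the operating room goes next.

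**The concern.** An observation window should not depend on the response being studied. Here, for patients who leave the operating room on Ang II, the ICU stay lasts at least as long as weaning takes. Slow weaners can supply urine output and intake on days 2 and 3; fast weaners may not. Later-day summaries would then describe a group selected partly for a poorer hemodynamic response.

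Urine output is not incidental to the rationale. Section 2 says perioperative catecholamine use is "associated with decreased urine output after kidney transplantation", and this is the first item in its list of harms. Section 9.0 also plans a multivariable regression on vasopressor duration and on a poorer kidney outcome that it does not define. If urine output were used as that outcome, how long it is observed would depend partly on the other outcome in the same analysis.

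**Working it through.** The plan gives no figure to reproduce. The check sets the collection windows side by side and follows what they imply.

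**Step 1: the windows in Section 6.0**

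| Postoperative item | Window | Tied to ICU? |
|---|---|---|
| BP, heart rate | hourly, at least 72 h | no |
| Volume resuscitation | 24, 48, 72 h | no |
| Creatinine, creatinine clearance, GFR | daily after surgery | no |
| Daily intake | ICU stay | yes |
| Daily urine output | ICU stay | yes |
| Blood products | ICU stay | yes |

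The BP and heart rate window can also lengthen with vasopressor use, but it never falls below 72 hours. The last three rows have no such floor.

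**Step 2: the link to response.** For a patient still on Ang II after surgery, ICU time is at least the time to come off vasopressors. That is a lower bound only. Without a discharge rule, other factors can lengthen the stay. The supported statement is that window length depends at least partly on vasopressor duration.

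**Step 3: what is lost.** Intake and urine output are daily, so length of stay changes how many values a patient has, not the size of each value. A 1-day stay gives 1 daily value and a 3-day stay gives 3 (stay lengths assumed). Day 1 is comparable among all patients in the ICU for that full day. Days 2 and 3 are available only for those still there.

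**Step 4: range for patients with no ICU stay.** The documents give 20 treated patients (Section 5.0) but not the share who never enter the ICU. Patients with no value = 20 × assumed share:

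- 0%: 20 × 0 = 0
- 10%: 20 × 0.10 = 2
- 25%: 20 × 0.25 = 5
- 50%: 20 × 0.50 = 10

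If the same assumed shares are applied instead to patients leaving the ICU after one day, those left with day-2 and day-3 values number 20, 18, 15 and 10. These are illustrations; the documents do not favour any of the non-zero shares.

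**Step 5: what is not affected.** The primary objective in Section 3.0 is judged by time to the BP goal and the secondary by adverse events. Neither uses these three items. The intake gap is partial, because resuscitation volume is recorded to 72 hours wherever the patient is. The blood-product gap is postoperative only, because "Intraoperative blood product utilization (volume and type of blood products administered" is listed separately.

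**The case against.** The strongest reply is that these are three descriptive items, that no named endpoint uses them, and that kidney function is well covered elsewhere. Creatinine is collected daily, at discharge and at 1 and 3 months, and the need for renal replacement therapy is recorded for the first year. Nothing says urine output defines the kidney outcome in Section 9.0. All of this stands and limits the weight of the point. It does not explain why three items lack the 72-hour window given to their neighbours.

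A reader might go further in three ways that the documents do not support:

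- **Totals inflated by a long stay.** One might infer that a patient with a longer stay would appear to pass more urine. The plan records daily volumes and nowhere plans a total over the stay. At a constant rate, each full day shows the same value however long the stay.
- **Patients weaned in the operating room go to a ward and have no data.** No section says so. The indirect evidence leans towards wider ICU care: the ICU team may manage postoperative hypotension in patients who had no intraoperative Ang II, ICU pH is recorded at 24, 48 and 72 hours if available, and the safety variables are described as routine in ICU care. Having no data is a possibility, conditional on no ICU stay.
- **Native urine mistaken for graft output.** Section 2 describes recipients as coming from dialysis, and the baseline list has no residual urine output. But the plan does not say how urine output will be interpreted, and the documents give no figure from which to size the effect.

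**Conclusion.** The point holds as a stated collection rule that makes later-day urine output, intake and postoperative blood products available only while the patient is in the ICU. For patients still on Ang II after surgery, that depends at least partly on the response under study. It is worth correcting but does not threaten the main results.

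The size cannot be fixed from the documents. If every treated patient stayed in the ICU for 72 hours, nothing would be lost over that period. If some left sooner, days 2 and 3 would be missing for them; if some had no ICU stay, all three items would be missing. The consequence is confined to descriptive reporting of these items and to the Section 9.0 kidney-outcome regression if urine output is used there. The conclusion rests on reading the ICU limit literally and on ICU time being at least as long as weaning for patients who continue Ang II there.

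**What to change.** In Section 6.0, for daily intake, daily urine output and postoperative blood products, replace the limit to the ICU admission with 0-24, 24-48 and 48-72 hours from the end of surgery, regardless of location. This brings them into line with the 72-hour span already used for blood pressure, heart rate and resuscitation volume. It also fixes the time origin, which the three items now leave unstated. Report the number of patients with a value in each interval.

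If urine output is to enter the Section 9.0 regression, name it there and use these fixed intervals. A baseline field for pre-transplant native urine output is optional; it would help in reading postoperative volumes, but the main correction does not depend on it.

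The cost is a wording change to three items and some extra extraction from ward flowsheets for patients who leave the ICU before 72 hours. Ward urine output may be charted less completely, so some intervals may still be missing. The charts must already be followed to 72 hours for hourly blood pressure and heart rate, so the added work is modest. Nothing in patient care changes.
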